#### **Selection of Subjects/Inclusion-Exclusion Criteria:**

Subjects (N = 50) will be healthy adults with age +/≥18 years and will be recruited from Duke University along with local community members. Subjects must verbally confirm the absence of any pre-existing skin conditions, skin allergies to tegaderm or other adhesive products contained within the study and control rings and pregnancy.

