**Study Objective:**

To determine whether the beeswax-pine resin mixture used in the LowCostomy buffer can be safely applied to intact human abdominal skin for the duration of a one-week period.

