#### **Design and Procedures:**

The purpose of this study is to examine the safety of the LowCostomy appliance's peristomal adhesive interface composed of a mix of beeswax and pine resin. Since this study is not directed at analyzing the efficacy of the entire LowCostomy system, only the beeswax mixture will be tested against test subjects' skin. Upon consultation with ostomy nurses, the peristomal skin was determined to be comparable to normal abdominal skin. Thus, rather than recruiting colostomy patients, the subject pool will include any willing healthy adults with age +/>>18 years (n=50). This subject pool must be heterogeneous in terms of ethnicity which ensures that a broad range of skin colors are being tested with the aim of removing bias toward a certain type or color of skin. The goal is to recruit 50% of subjects who self-identify as having a medium to dark skin tone and 50% who self-identify as having with a light skin tone. Subjects will be given \$50 as compensation.

Each study subject will be tested with two thin rings of the beeswax-pine resin formula—one being a domestic beeswax-pine sample while the other ring will be a Tanzanian beeswax-pine sample. Using both a domestic and international sample, we can test whether regional differences in these products might yield significantly different results. Such beeswax-pine samples will be tested alongside a control adhesive in the form of Hollister's AdaptTM Barrier Rings. The length of the study will be 7 days. The beeswax-pine ring will be created to match the dimensions of the control (width: 4.5 mm, outer diameter: 48 mm). The beeswax-pine buffer will be composed of the same beeswax-pine resin ratio that will be used in the LowCostomy appliance's overall design. Such tests will be performed on the subjects' abdomen. Prior to application, a licensed physician will record observations concerning the condition of the abdominal skin including color, odor, texture, and hygiene. Pictures will be obtained for documentation purposes as well using a Nikon D5600, 24.2M pixel camera. During picture taking we will limit identification by choosing an area of skin with limited identifying marks or tattoos. The camera will automatically date stamp the picture however, there will be no other identifiers captured. A single dedicated camera will be used for all photos. At the screening visit on Day 1, a member of the research team will obtain a current medication

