list and a medical history regarding known pre-existing skin conditions and history of skin reactions to elements of the study and control adhesive rings, to validate that there are no additional associated risks with participating in this study. If the area of application is too hairy to obtain a clear view of the skin, the healthcare professional will shave the pertinent area. The three areas of application will be marked with a medical marker to ensure even and consistent placement of the samples. A measurement device will be included in each picture for documentation and quantification of adverse skin reactions. The control ring will be applied according to the manufacturer's instructions; the beeswax-pine rings will be placed in a similar fashion but in addition, will need to be massaged against the skin to build friction and heat, allowing for a more effective adhesion. To fully seal the rings with the skin, Tegaderm will be placed over the rings, which allows the study subject to shower over the 7-day period with minimal interference with the study results. If the initial adhesives are not able to endure the full 7 days due to adhesive or application failure, such results will be noted and excluded from final analysis.

Each subsequent day after the initial placement of the samples, the subject will be asked to remove the tegaderm and the three adhesive rings briefly for less than 20 minutes, then promptly reapply in the exact same location with new tegaderm. The act of daily removal and reapplication of the samples will simulate

the typical routine of colostomy patients as they remove and reapply their ostomy products.

Twenty-four pieces of tegaderm will be provided per subject for the purpose of reapplying the samples. During the education session, subjects will be shown how to properly apply tegaderm over the three samples. Subject participation ends at Day 7.

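### Day 1 skin findings and the medication list do not decide entry, so users of anti-inflammatory or anti-itch drugs can enrol and shrink any difference from the control ring

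*Protocol*

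**What the plan says.** The Study Objective asks whether the mixture "can be safely applied to intact human abdominal skin for the duration of a one-week period". Purpose of the Study defines safe as irritation or injury no greater than with standard commercial products such as the control ring.

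Under Selection of Subjects/Inclusion-Exclusion Criteria, subjects are healthy adults. The condition on skin is: "Subjects must verbally confirm the absence of any pre-existing skin conditions". They also confirm verbally that they have no allergy to the adhesives and are not pregnant. Subject Recruitment and Compensation adds that interested people who meet the criteria may take part.

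Design and Procedures describes two further sources of information on Day 1:

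- **Skin.** "Prior to application, a licensed physician will record observations concerning the condition of the abdominal skin including color, odor, texture, and hygiene". No finding is made a reason to move a site or not to enrol.
- **Medication and history.** A team member lists the medicines in current use and asks about skin conditions and past reactions to ring components. The stated purpose is "to validate that there are no additional associated risks with participating in this study".

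The outcomes are Draize grades from Day 1 and Day 7 photos and the 5-D itch scale. Each subject wears two test rings and one control ring, and the plan is to look for significant differences between the samples. Data and Safety Monitoring provides a survey at the end of each day. No section addresses anti-inflammatory or anti-itch drugs, at entry or during the week.

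**The concern.** The trial measures redness, irritation and itch. A drug that suppresses these acts on the outcome itself, whether or not its user has a skin condition. Someone taking a daily antihistamine for hay fever can truthfully confirm that they have no skin condition and be enrolled.

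The three rings share one abdomen, so a systemic drug works on all of them at once. It does not favour one ring through imbalance, but it compresses whatever difference exists. When the claim is no greater irritation than control, and the evidence is a search for significant differences, lost sensitivity helps the claim.

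There is a second, smaller gap. The objective is limited to intact skin, yet nothing in the criteria requires anyone to confirm by examination that the marked sites are intact.

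**Working it through.** **Setting the sections side by side**

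| Information on Day 1 | Stated use | Decides entry for outcome validity? |
|---|---|---|
| Verbal confirmation of no skin condition (Selection of Subjects) | Eligibility | Yes, but self-report only |
| Physician's skin observation (Design and Procedures) | Recorded | No |
| Skin and reaction history (Design and Procedures) | Participant risk | No; also self-report |
| Medication list (Design and Procedures) | Participant risk | No |
| Day 1 photo (Data Analysis and Statistical Considerations) | Draize grade | No, but gives a graded baseline |

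There is no plan figure to reproduce. The Protocol gives N = 50 without a margin, effect size, standard deviation or power. The calculations below use assumed inputs and show direction and rough scale only.

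**1. Dilution of a difference in proportions.** Let f be the share of subjects whose reactions are fully suppressed. A true excess of 10 percentage points over control is seen as 10 × (1 − f):

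- f = 5%: 10 × 0.95 = 9.5 points
- f = 10%: 10 × 0.90 = 9 points
- f = 20%: 10 × 0.80 = 8 points

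If the drug removes only half the difference, the factor is 1 − 0.5f, which gives 9.75, 9.5 and 9 points.

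**2. Power for a paired continuous comparison.** Inputs: n = 50 from the Protocol; two-sided alpha 0.05 and a standardized within-subject difference d = 0.40, both assumed. Power = Φ(d(1 − f·s)√50 − 1.96), where s is the share of the difference that the drug removes. For f = 0: 0.40 × 7.071 − 1.96 = 0.868, so power is 80.7%.

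| f | s = 1 (whole difference removed) | s = 0.5 (half removed) |
|---|---|---|
| 0 | 80.7% | 80.7% |
| 10% | 72.1% | 76.6% |
| 20% | 61.9% | 72.1% |

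The standard deviation is held fixed. If suppressed subjects contribute differences near zero, the spread shrinks too, and these losses are overstated.

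**3. Power for a paired binary comparison.** Exact two-sided McNemar test, n = 50, assuming irritation at the test ring only in 25% and at the control ring only in 5%, both multiplied by (1 − f). Power is 69.9% at f = 0, 63.6% at f = 10% and 56.6% at f = 20%.

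All three calculations move towards missing a true difference. The amount depends on f and s, which the Protocol does not give.

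**The case against.** The case on the other side has real force.

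- **Screening exists.** A reader might infer that nothing stands between a spoken statement and enrolment. That is too strong. There is a Day 1 screening visit with a physician's observation, a history and a medication list, and the pool is limited to healthy adults. This makes users of systemic corticosteroids or other immunosuppressants unlikely. It leaves antihistamine users, because healthy is not defined and Risk/Benefit Assessment itself allows that an ostomy patient might take part. What is missing is a rule linking the information to entry.
- **Baseline irritation is graded.** Day 1 photos receive a Draize score, so a site irritated at entry can be identified, and its handling may sit in the analysis plan. This stands, and it makes the skin half of the point the lesser one.
- **Not everything pushes towards safe.** A reader might infer that baseline redness always favours the test rings. The Protocol does not support that. It plans comparisons between samples and states no change-from-baseline endpoint. Redness common to all three sites largely cancels, and redness at one site can bias either way depending on which ring sits there.
- **Shaving and score ceiling.** One might argue that "the healthcare professional will shave the pertinent area" creates unrecorded redness, or that an irritated site has less room to worsen on the Draize scale. Neither holds on the text. Shaving is meant to give a clear view of the skin and plausibly precedes the Day 1 photo. The Protocol does not state the range of the scale, and nothing suggests that reactions would come near its top.
- **The effect is modest.** With f = 10%, the 10-point excess falls by only 1 point even under full suppression. This stands as a limit on size.

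The medication gap remains. Pairing cannot restore a difference that a drug has suppressed, a Draize baseline does not reveal drug use, and no Day 1 itch assessment is described.

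**Conclusion.** The point holds in a limited form. Eligibility is a matter for the Protocol, and as written it admits users of drugs that can blunt both outcomes. The resulting loss of sensitivity favours a conclusion of no greater irritation.

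The size is unknown and probably modest: 9.5 to 8 points observed for a true 10, if 5% to 20% of subjects were fully suppressed. Both the shares and full suppression are assumptions, and partial suppression gives less. Irritation present on Day 1 is a secondary matter of uncertain direction, worth settling mainly because the objective is confined to intact skin. This is an inexpensive improvement that should be made. It does not show that the trial would reach a wrong conclusion.

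**What to change.** Amend Selection of Subjects/Inclusion-Exclusion Criteria so that information already collected on Day 1 decides entry.

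1. **Skin.** The physician's existing Day 1 examination confirms, after any hair removal, that each marked site is intact and free of visible irritation. If a site is not, another is chosen or the subject is not enrolled that day. A live Draize score is not needed.
2. **Medication.** The existing list is used not to enrol current users of drugs expected to suppress skin inflammation or itch. The sponsor defines which drugs count. Nobody is asked to stop a treatment in order to take part.
3. **During the week.** One item on new use of such drugs is added to the existing daily survey, with a sensitivity analysis that excludes users. New use may be a response to a ring reaction, so this analysis should stand beside the analysis of all subjects and not replace it.

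The cost is protocol wording, a short confirmation step at an examination that already takes place, one survey item and one extra analysis. No visit is added. The downside is some additional screen failures, mainly antihistamine users, and a slightly narrower population.

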#### **Subject Recruitment and Compensation**

Potential participants will be recruited from the community. Advertising materials in the form of flyers that contain a QR code directing interested participants to the study's website will be placed around Duke's campus and clinical settings as well as broader public spaces. Additionally, Duke's ListServ email system will be utilized to recruit participants. Potential participants that express interest will be contacted by phone to further discuss study details, answer questions, review pertinent eligibility criteria, and preschedule study activities. Potential participants will not be contacted more than three times, including via letter, phone, email, and face-to-face interaction. If a participant states they would like to opt out, the study team will follow the Duke Recruitment and Engagement policy. Those who are

interested will be able to participate if they meet inclusion and exclusion criteria. A minimum of 50 subjects will be recruited. Incentive payment for subjects to participate in the study will be \$50.

**Subject's Capacity to Give Legally Effective Consent:**

The study will not include subjects without the capacity to give legally effective consent.

**Risk/Benefit Assessment:**

The main risk of the study is a reaction or skin irritation caused by the beeswax-pine resin mixture. This could include an allergic reaction, local skin irritation, redness, itchiness, or in severe cases blistering. Based on background research of existing beeswax-pine resin products, it has been hypothesized that a reaction is unlikely, but still possible. If a reaction occurs that is too uncomfortable to continue the study for the entire 7 days, the subject may stop early, and the reaction will be noted. The risks of the study are not being borne by the likely beneficiaries. The test subjects will likely not gain any health benefits from participating in the study; such subjects are not colostomy patients and hence not the target consumers of the LowCostomy appliance. Further, if an ostomy patient happens to participate in the study, he/she will likely return to the use of higher-priced medical-grade colostomy appliances without the use of the beeswax-pine resin mixture as the LowCostomy device will be marketed to populations in low-resource settings. The analysis expected to result from the tests is more valuable to the target low-income patients of Sub-Saharan Africa, who would be using this mixture on their skin. This is the main purpose of providing a monetary incentive to American patients who participate.

The loss of privacy and confidentiality is an additional risk. However, every reasonable effort will be made to limit breaches of privacy and confidentiality.

**Costs to the Subject:**

There will be no costs to the subjects. All necessary supplies will be provided for the duration of the study.

**Data Analysis and Statistical Considerations**

Data from subjects who successfully complete the seven-day study will be used for analysis. The photos from Day 1 and Day 7 will be reviewed by the licensed physician using the Draize skin scoring system. Subjects will fill out a survey of their experiences of wearing the beeswax-pine resin adhesive. The 5-D itch scale will be used to quantify subjective experiences. All photos included in the dataset will be blinded before a licensed physician quantitatively indicate the level of skin irritation. Only the data of subjects who completed data collection for the entire 7-day duration will have their results quantified. Statistical tests will be completed on the results to draw conclusion about whether the beeswax-pine resin samples, in comparison to our control, caused skin irritation.

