**Data and Safety Monitoring**

Adverse side effects of the beeswax-pine resin mixture placed on the skin may include redness, rash, skin irritation, and infection. In the duration of the seven-day period, subjects will be provided a survey at the end of each day to assess their overall well-being and to provide them a space to express any concerns they may have. Any significant infection or irritation of the skin that causes serious concern for the subject will be evaluated by a licensed physician to evaluate whether they can continue in the study. Any signs of infection or other adverse side effects will result in the immediate cessation of the seven-day period for that subject.

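### The comparison with control is limited to seven-day completers, yet skin reactions, which are the outcome, can end participation, so the result that decides safety can be biased

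*Protocol*

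**What the plan says.** Data Analysis and Statistical Considerations states the analysis set twice: "Data from subjects who successfully complete the seven-day study will be used for analysis", and later "Only the data of subjects who completed data collection for the entire 7-day duration will have their results quantified". The same section draws the conclusion on irritation relative to control from those results. Purpose of the Study defines safe as irritating or injuring the skin no more than a commercial ostomy product, with no numerical margin.

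Three statements let a skin reaction end participation, and they differ:

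- Risk/Benefit Assessment leaves the choice to the subject. If a reaction is too uncomfortable, "the subject may stop early, and the reaction will be noted".
- Data and Safety Monitoring sends infection or irritation that seriously concerns the subject to a physician. Such a reaction "will be evaluated by a licensed physician to evaluate whether they can continue in the study".
- The same section then states an automatic rule: "Any signs of infection or other adverse side effects will result in the immediate cessation of the seven-day period for that subject". It has already said what such effects are: "Adverse side effects of the beeswax-pine resin mixture placed on the skin may include redness, rash, skin irritation, and infection".

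Under Design and Procedures each subject wears two beeswax-pine rings and one control ring. Draize grading uses blinded photos planned for Day 1, before application, and Day 7 only. Reactions can also be reported to a study contact, and "subjects will be provided a survey at the end of each day to assess their overall well-being".

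**The concern.** The signs that can end participation (redness, rash, irritation) are those the Draize grading is meant to measure. A completer-only set therefore selects subjects on the outcome. The within-subject design does not protect against this: a stop caused by one ring deletes all three readings for that subject, including the contrast that led to the stop.

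What is at stake is the main conclusion. If the beeswax-pine rings are in truth more irritating, losing the subjects who show it can make them look no worse than control, which is the harmful error in a safety study. The protocol itself ties the expected reactions to the test material: "The main risk of the study is a reaction or skin irritation caused by the beeswax-pine resin mixture". The case in which mainly beeswax-pine reactors stop therefore cannot be set aside.

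**Working it through.** **Inputs from the protocol.** At least 50 subjects, three sites each, completers only, photos on Days 1 and 7. It gives no reaction rate, stopping rate or margin and no derivation of the sample size, so there is no stated figure to reproduce.

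**Assumptions.** The outcome is simplified to reaction yes/no per ring. Let p_b be the reaction probability at each beeswax-pine ring, p_c that at the control ring, d = p_b − p_c, and s the share of the named group who stop. All values are illustrative. Among completers, for one test ring against control:

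D = [P(test ring reacts and subject completes) − P(control reacts and subject completes)] / P(subject completes)

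**1. Stopping equally likely whichever ring reacts.** D = d(1 − s)/(1 − sR), where R is the probability that at least one of the three rings reacts. R = 1 − (1 − p_b)²(1 − p_c) if the sites are independent; R = max(p_b, p_c) if the reactions are fully nested.

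- 20% vs 5%, s = 0.5, independent: R = 1 − 0.64 × 0.95 = 0.392, so D = 0.075/0.804 = 9.3 points. Nested: 0.075/0.90 = 8.3. True value: 15.
- 5% vs 2%, s = 0.5, independent: R = 1 − 0.9025 × 0.98 = 0.116, so D = 0.015/0.942 = 1.6. Nested: 0.015/0.975 = 1.5. True value: 3.
- s = 1: D = 0 whatever the true rates.

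A different stopping model, in which each reacting site separately leads to a stop with probability s, gives the same pattern. The completer rate at an independent site is then p(1 − s)/(1 − ps). At 20% vs 4% and s = 0.5 it is 0.10/0.90 − 0.02/0.98 = 9.1 points against a true 16.

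**2. Only beeswax-pine reactors stop.** Independent sites: D = p_b(1 − s)/(1 − sR_w) − p_c, with R_w = 1 − (1 − p_b)². At 20% vs 5%, R_w = 0.36.

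- s = 0.5: 0.10/0.82 − 0.05 = 7.2 points. Nested: 8.3.
- s = 1: 0 − 0.05 = −5 points. Nested: 0.
- With independent sites the sign reverses once s exceeds 0.15/(0.20 − 0.05 × 0.36) = 0.15/0.182 = 82%.

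**3. Only control reactors stop, all of them.** At 20% vs 5%: independent 0.20 − 0 = 20.0 points; nested 0.15/0.95 = 15.8. The difference grows.

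**4. These ranges are not limits.** If reactions at the three sites exclude one another, case 2 at 20% vs 5% gives 0.10/0.80 − 0.05/0.80 = 6.25 points at s = 0.5 and (0 − 0.05)/0.60 = −8.3 points at s = 1. Both lie outside the figures in step 2.

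**5. Subjects lost.** The expected number of stoppers in case 1 is 50sR. At s = 0.5 this is 1.25 (nested) to 2.9 (independent) at 5% vs 2%, and 5 to 9.8 at 20% vs 5%.

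**The case against.** **No bias is certain.** A reader might infer that the comparison is biased, or biased in favour of the new material. The documents do not support either as a fact. If nobody stops for a reaction there is no bias from this source. If the rings react at equal rates and stopping is symmetric, the difference stays at zero, although both absolute rates are understated. The direction depends on who stops. The protocol expects reactions to be unlikely, and at 5% vs 2% with half of reactors stopping the shift is about 1.4 to 1.5 points, less than one subject in 50. This stands, and the point is worded accordingly.

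**Reactors may still reach Day 7.** Under the physician-evaluation route, subjects with mild irritation may continue and contribute Draize scores. A reaction first seen on Day 7 is also retained. This stands, so the zero difference in step 1 applies only if every reactor stops, as the automatic rule read literally requires once a reaction is noticed.

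**The reactions are not lost.** They are noted, can be reported, and may appear in the daily surveys. That is correct, and it would be wrong to say that the study discards the signal. But no section brings those records into the comparison with control.

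**The SAP may deal with it.** The SAP was not available for this review. It could add a sensitivity analysis, but the protocol positively fixes the completer set, so a primary analysis of all subjects with rings applied would contradict it.

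**Adhesive failure.** A reader might extend the point to the exclusion of rings that fail to adhere (Design and Procedures). Nothing in the protocol shows that such failures depend on skin reactions, so this is not part of the point.

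**Conclusion.** The concern holds in conditional form. The protocol states a rule under which the outcome can remove subjects from the comparison that decides safety, and no other section repairs it. The comparison can therefore be biased: toward zero if stopping is symmetric across rings, past zero in favour of the test rings if mainly beeswax-pine reactors stop, or away from zero if mainly control reactors stop. The completer data cannot show which case applies.

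The size is unknown. The figures of 15 becoming about 8 to 9 points, and 3 becoming about 1.5, rest on assumed rates, a yes/no outcome and half of all reactors stopping. They show what is possible, not what is likely. The point should be settled before enrolment, because a photo not taken at the time of stopping cannot be recovered later.

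**What to change.** Replace both completer sentences in Data Analysis and Statistical Considerations with wording to this effect:

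> The primary comparison includes all subjects who had rings applied. For a subject who stops early, the Day 7 photo and survey are brought forward to the time of stopping, and the blinded Draize grade of that photo is the outcome for each site. If a subject stops for a reaction and has no stopping photo, the reacting site or sites, as recorded at the time of stopping, receive a prespecified unfavourable score or rank, with alternative values as sensitivity analyses. The pre-application Day 1 photo is not carried forward as an outcome. Stops for other reasons without a photo are treated as missing. The completer analysis is a sensitivity analysis.

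Because the comparison is paired, the prespecified rule should also say what value the other sites of a reaction stopper without a photo receive.

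Separately, the sponsor must reconcile the differing stopping statements in Risk/Benefit Assessment and Data and Safety Monitoring. This review takes no position on which should apply.

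**Cost.** No extra subjects are needed. The photo visits are unscheduled: with half of reactors stopping, about 1 to 3 of 50 subjects at 5% vs 2% and 5 to 10 of 50 at 20% vs 5%. The other downsides are unequal exposure time among stoppers, unblinded attribution of a reaction to a ring where no photo exists, and a possibly less favourable safety result.
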